Cover page

The Clinical Investigation plan for study **CP319**

A clinical pilot study of newly developed ostomy tapes and how they adhere to the skin.

NTC ID: 04544566

Document date: 12/11/2020

Clinical Investigation Plan

CP319

A clinical pilot study of newly developed ostomy tapes and how they adhere to the skin

March 2020 – August 2020

This confidential document is the property of Coloplast A/S.
No unpublished information contained herein may be
disclosed without written approval of Coloplast A/S.

SYNOPSIS OF THE CLINICAL INVESTIGATION

Aim and objective(s)

The aim of the study is to explore different recipes of ostomy tapes and understand their ability to adhere to the skin without affecting it.

The primary objective is to explore the adherent area after use.

Secondary objective is to explore the skin after application of the ostomy tapes.

Design of the investigation

This investigation is a randomised, open-label, comparative, cross-over study, with three test periods. In total, 12 subjects will be included and randomised, and each subject will have an inclusion visit and four test visits overseen by the Principal Investigator, or delegate. Each subject will be enrolled for three times 7-9 days in total for the entire investigation, thus for a maximum of 27 days – equal to at least 3 baseplates + tape change in each period. The subjects will test two new recipes of ostomy tapes and a comparator product in randomised order.

Between visits the subject will change products at home. At each product change every user should record experience at home by taking picture of the peristomal skin, and answer questions. All tapes should be removed from the baseplate and saved for the next visit at CP.

Test products and comparator

The test products are non-CE marked stoma tape products. The two test products are adhesive strips designed to support the edges of the ostomy baseplate by providing additional adhesion to the intact peristomal skin.

The comparator is [REDACTED].

Primary endpoint and secondary endpoint(s)

Primary endpoint:

- Mean adherent area measured by photo of used tape (area (cm²) per baseplate change)

Secondary endpoints:

- Erythema measured after each treatment period by spectrophotometric method
- Erythema measured after tape removal by photos
- Feeling of security
- Adhesion of tape
- Comfort
- Skin issues in the area covered by the tape
- Adverse Events

User experience with feeling of security, adhesion of tape, comfort and skin issues in the area covered by tape, will be assessed by interviews at Coloplast visit and self-reported by user at home.

Population/subjects

The population in this investigation includes 12 subjects with an ileostomy, colostomy or urostomy that comply with the following in- and exclusion criteria:

Inclusion criteria	Exclusion criteria
Has given written informed consent	Currently receiving or have within the past 2 months received radio-and/or chemotherapy
Be at least 18 years of age and have full legal capacity	Currently receiving or have within the past month received topical steroid treatment in the peristomal skin area or systemic steroid (tablet/injection) treatment
Have had a stoma for more than ½ year	Is pregnant or breastfeeding
Have intact skin on the area used in the study (Assessed by investigator, see Appendix 1.).	Having dermatological problems in the peristomal area (assessed by investigator)
Willing to change baseplate every second day or less frequent	Currently receiving or have within the past 2 months received radio-and/or chemotherapy
Willing to avoid using Concave baseplate during the study.	Currently receiving or have within the past month received topical steroid treatment in the peristomal skin area or systemic steroid (tablet/injection) treatment
Willing to avoid the use of barrier creams or similar that affect the skin/adhesive interface under the tape.	Is pregnant or breastfeeding

Investigation approval

The investigation will be approved by the Ethical committees and the competent authorities before investigation initiation.

> **TABLE OF CONTENTS**

1. List of personnel involved in the Investigation	8
1.1. Sponsor representatives	8
1.2. Investigators.....	8
2. Rational/justification for conducting the clinical investigation	8
3. Objective(s) of the clinical investigation	9
4. Investigational device and comparator(s)	9
4.1. Description of investigational device	9
4.1.1. Manufacturing	9
4.2. Identification and traceability of the device	9
4.3. Intended use of the device in the clinical investigation	9
4.4. Intended population for the device	9
4.5. Handling of the investigational device	9
4.6. Description of the comparator product(s).....	10
5. Design of the clinical investigation	10
5.1. General	10
5.2. Primary endpoint.....	10
5.3. Secondary endpoints.....	10
5.4. Rationale for selection and measurement of endpoints	11

1.2. Investigators

The Clinical Manager is responsible for maintaining an updated list of all PIs, investigation sites and institutions.

PRINCIPAL INVESTIGATOR
[name]
[REDACTED]

2. Rational/justification for conducting the clinical investigation

People with abdominal stomas have, despite development of better ostomy products, still problems with leakage and peristomal skin disorders which influence their quality of life negatively [1,2].

To minimize the risk of leakage on clothing, ostomy tape can be used. [REDACTED] and is used to support the rim of the ostomy base plate/adhesive by providing additional adhesion to the intact peristomal skin.

The adhesives in the ostomy tapes are developed to make the tape seal to the skin and thereby minimise the risk of leakage episodes. At the same time, the tape should be easy to remove without affecting the skin.

This evaluation investigates two newly developed adhesives and their ability to adhere to the skin without affecting it. Based on the knowledge obtained in this investigation, an improved ostomy tape can be developed and thereby give ostomists new supporting products that reduce the risk of leakage episodes.

3. Objective(s) of the clinical investigation

The purpose of the study is to explore different recipes of ostomy tapes and understand their ability to adhere to the skin without affecting it.

The primary objective is to explore the adherent area after use.

Secondary objective is to explore the skin after application of the ostomy tapes.

4. Investigational device and comparator(s)

4.1. Description of investigational device

The test products are non-CE marked stoma tape products. The products are adhesive strips designed to support the edges of the ostomy baseplate by providing additional adhesion to the intact peristomal skin. [REDACTED]

[REDACTED]

[REDACTED]

[REDACTED]

[REDACTED]

[REDACTED]

4.1.1. Manufacturing

4.2. Identification and traceability of the device

For this study the test products are packed in GRIPPIE zip lock bags (LDPE). Labels are placed on these bags. [REDACTED] (standard of care) used in CP319 is already CE marked and is labelled accordingly.

4.3. Intended use of the device in the clinical investigation

The product is intended to support the rim of the ostomy base plate/adhesive by providing additional adhesion to the intact peristomal skin.

4.4. Intended population for the device

Brava Tape Innovation is indicated for people who use an ostomy bag and base plate/adhesive. The product is indicated for both male and female adults.

4.5. Handling of the investigational device

The handling of the test products is described in details in the Instruction for Use (IFU), which is included in all bags with test products. It is stated in the IFU that the test products are for single-use and must be stored horizontally under dry and not freezing conditions and should be kept away from direct sunlight.

4.6. Description of the comparator product(s)

The comparator product is [REDACTED] which is already on the market and will be used within the intended use in this clinical investigation. Therefore, it is not considered an investigational device according to ISO 14155:2011 and is thus not described here. Please refer to the ISO 14155:2011 for details.

5. Design of the clinical investigation

5.1. General

This investigation is a randomised, open-label, comparative, cross-over study, with three test periods.

In total, 12 subjects will be included and randomised, and each subject will have an inclusion visit and four test visits overseen by the Principal Investigator, or delegate. Each subject will be enrolled for three times 7-9 days in total for the entire investigation, thus for a maximum of 27 days – equal to at least 3 baseplates + tape change in each period. The subjects will test two new recipes of ostomy tapes and a comparator product in randomised order.

Between the test visits, the subjects will change products at home. At each product change, subjects will take a photo of the peristomal skin using a smartphone with a specially designed Clinical Trial app installed. Furthermore, they will answer questions about feeling of security, adhesion of tape, comfort and potential skin issues.

5.2. Primary endpoint

- Mean adherent area measured by photo of used tape (area (cm²) per baseplate change)

5.3. Secondary endpoints

- Erythema measured after each treatment period by spectrophotometric method
- Erythema measured after tape removal by photos
- Feeling of security:
 - How was the feeling of security while wearing the tape?
(5-point scale from Very poor to Very good)
 - Did you feel confident that the tape would keep your base plate securely in place?
(5-point scale from Very little to Very much)
- Adhesion of tape:
 - How was the immediate adhesion to the skin?
(5-point scale from Very poor to Very good)
 - Did the edge of the tape lift/roll during use?
(5-point scale from Very poor to Very good)
- Comfort:
 - How comfortable was the tape to wear?
(5-point scale from Very uncomfortable to Very comfortable)
 - Did the tape allow you freedom of movement?
(5-point scale from Very little to Very much)
- Skin issues in the area covered by the tape:
 - Do you experience any **bleeding from the skin** under the tape right now when changing your product? (Experiencing/Not experiencing)
 - Once you have cleaned and dried the skin, do you experience any **weeping or moisture on the skin** under the tape right now when changing your product? (Experiencing/Not experiencing)
 - Are you experiencing any **ulcers or sores** under the tape right now when changing your product? (Experiencing/Not experiencing)
 - Did you experience complications where the tape was applied (like pain, stinging, itching, heat swelling or shiny skin)? (Yes/No)

- Please rate how painful the skin under the tape has been at its worst, since you last changed your product. (10-point scale from no pain (1) to worst pain possible (10))
- Please rate how itchy the skin under the tape has been at its worst, since you last changed your product. (10-point scale from no itch to worst itch possible)
- Adverse events

User experience with feeling of security, adhesion of tape, comfort and skin issues in the area covered by tape, will be assessed by prior mentioned questionnaires which will be assessed by interviews at Coloplast visit and self-reported by user at home.

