5.4. Rationale for selection and measurement of endpoints

The endpoints are parameters describing the adherence of the ostomy tape to the skin and the potential effect on the skin. These are essential to investigate to understand, if the newly developed ostomy tapes have the ability to adhere to the skin without affecting it.

Adherent area: The adherent area after use shows how effectively the ostomy tape adheres to the skin. After removal of the ostomy tape, a photo of the tape is taken. The adherent area is measured from the photo and an image analysing program.

Erythema: A change in the surface skin colour is known to be related to a change in the blood flow. This can be measured non-invasively with a spectrophotometric instrument (Derma-spectrophotometer, Cortex Technology A/S, Hadsund) where both the redness and the colour of the skin are measured. Furthermore, visual assessments of photos have been used in several exploratory clinical investigations by Coloplast A/S to explore how adhesives affect the skin. The visual assessment is conducted by trained personnel and is a valuable tool for assessing newly developed adhesives and their impact on skin in the early development phases.

Feeling of security, adhesion of tape, comfort and skin issues: User experience is a very important part of product development in Coloplast A/S, and questions related to feeling of security, adhesion of tape and comfort relate to the user experience of how the ostomy tape adhere to skin while questions regarding skin issues relate to how the ostomy tape affects the skin.

Adverse Events: All Adverse Events are captured and documented throughout the study.

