- Ostomy tapes are removed with use of adhesive remover (before removing, mark the lifted tape area with a pen on the adhesive part)
- Photo of peristomal skin (digital camera)
- Photo of skin (smartphone – Clinical Trial App)
- Smartphone: Questionnaire about feeling of security, adhesion of tape, comfort & skin issues in the area covered by the tape
- Acclimatization of peristomal skin for ½ hour
- Photo of peristomal skin after acclimatization (digital camera)
- Measurements of erythema
- Application of stoma product which subject normally use
- Collect all used tapes and measure the adherent area
- Review AEs/ADEs/SAEs/SADEs
- Collect smartphone
- Possibility to accept interview by User Insight/development engineers/project members
- Fill in termination form

Product change and study specific procedures, to be followed at home:

Between visits the subject will change at home. At each product change, the subject should record experience at home by taking photo of the peristomal skin and answer questionnaires (with a Clinical Trial app on a handed-out smartphone).

At home:

- a) Remove tape with use of adhesive remover (before removing mark the lifted tape area with a pen on the adhesive part).
- b) Remove the tape from baseplate and save the tapes in the provided storage material for the next visit
- c) Take photo of peristomal skin.
- d) Answer questions (about feeling of security, adhesion of tape, comfort & skin issues in the area covered by the tape)

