7.3. Flow-chart

Table 3 chart showing the connection between visits and assessments.

	PERFORMED BY	BASELINE	TEST PERIOD	TEST PERIOD	TEST PERIOD	TERMINATION
VISIT WINDOW (DAYS)	-	-	-	7 - 9	7 - 9	7 - 9
GENERAL						
Subject information	Investigator	X				
Signed informed consent	Subject / Investigator	X				
Signed letter of authority	Subject / Investigator	X				

Allocation of subject number	Investigator	X				
Check of in- and exclusion criteria	Investigator	X				
Visual evaluation of skin for inclusion	Investigator	X				
Pregnancy test, dipstick (If applicable)	Investigator	X				
Randomization	Investigator		X			
Insurance of subjects' wellbeing and compliance with CIP	Investigator	X	X	X	X	X
COLLECTION AND REGISTRATION OF BASELINE DATA						
Demographics: Gender, age, height and weight	Investigator	X				
Stoma: Type, reason and duration	Investigator	X				
Use of ostomy tape (Y/N)	Investigator	X				
Use of other accessories (Ring and paste)	Investigator	X				
Usually stoma product used	Investigator	X				
Optionally interviews	Development engineers/project members			X	X	X
PROCEDURES						
Instruct in and follow up on subjects use of smartphone and Clinical Trial app	Investigator		X	X	X	X
Remind the subject to bring the smartphone at every study visit	Investigator		X	X	X	X
Mark the lifted tape area with a pen on the adhesive part, before removing the ostomy tapes	Investigator			X	X	X
Remove tape/product with use of adhesive remover.	Investigator		X	X	X	X
Photo of peristomal skin (digital camera)	Investigator		X	X	X	X
Photo of peristomal skin (smartphone)	Subject			X	X	X
Acclimatize peristomal skin for ½ hour	Subject		X	X	X	X
Smartphone, Questionnaire: Feeling of security, adhesion of tape and comfort	Subject			X	X	X
Smartphone, Questionnaire: Skin issues in the area covered by the tape	Subject			X	X	X
Photo of peristomal skin, after ½ hour acclimatization (digital camera)	Investigator		X	X	X	X
Measure erythema	Investigator		X	X	X	X
Provide test products to the subject	Investigator		X	X	X	
Apply ostomy product and ostomy test tapes (Test tapes should be applied at the edges of the baseplate)	Subject		X	X	X	
Provide storage material for used ostomy tapes and adhesive remover	Investigator		X	X	X	
Instruct and remind the subject to follow the study specific procedures between visits	Investigator		X	X	X	X

Schedule next visit	Investigator	X	X	X	X	
Collect all used tapes and measure the adherent area by photography	Investigator			X	X	X

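### The edge lift/roll question in section 5.3 has response anchors that do not answer it, so the meaning of a high rating is not certain

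*Combined protocol and SAP*

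**What the plan says.** Section 5.3 lists tape adhesion among the secondary endpoints and measures it with two 5-point items. One asks about adhesion immediately after application. The other asks "Did the edge of the tape lift/roll during use". Both carry a "5-point scale from Very poor to Very good".

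The two other 5-point items that open with *Did* (confidence that the baseplate is held, and freedom of movement) use a "5-point scale from Very little to Very much".

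The questions are to be "assessed by interviews at Coloplast visit and self-reported by user at home". The flow-chart in 7.3 has a row "Smartphone, Questionnaire: Feeling of security, adhesion of tape and comfort" and gives the subject as the person who performs it. Section 5.4 says that the questions on security, "adhesion of tape and comfort relate to the user experience of how the ostomy tape adhere to skin".

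Section 10.1 has every individual question listed and summarised descriptively, separately by product. It assigns no numbers to the 5-point categories and does not say which end is favourable.

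**The concern.** Read literally, the item has no usable answer. A subject whose tape stayed flat cannot say *not at all*, and one whose tape lifted badly cannot say *a lot*. Each must decide what a quality rating of lifting means. Most will probably treat *Very good* as a good result. A subject who has just answered the other *Did* items as questions of extent could instead give a high answer to mean much lifting.

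Because every subject tests all three products, a subject who consistently reads the scale in reverse reverses their own contrast between products. It would be hard to see in the data, since any rating from *Very poor* to *Very good* is a valid entry. This is also the only self-reported item under the adhesion heading that covers the wear period rather than the moment of application, and it will be reported on its own for each product.

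**Working it through.** **Step 1. Set each 5-point question in section 5.3 against its anchors.**

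| Topic of question | Form | Anchors | Do they answer it? | High end |
|---|---|---|---|---|
| Security while wearing | How | Very poor – Very good | Yes | Favourable |
| Confidence that baseplate is held | Did (extent) | Very little – Very much | Yes | Favourable |
| Immediate adhesion | How | Very poor – Very good | Yes | Favourable |
| Edge lift/roll | Did (unwanted event) | Very poor – Very good | **No** | Not stated |
| Comfort | How | Very uncomfortable – Very comfortable | Yes | Favourable |
| Freedom of movement | Did (extent) | Very little – Very much | Yes | Favourable |

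Five of six match; one does not. Question and anchors are adjacent and intact, so neither redaction nor text extraction explains the mismatch.

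**Step 2. Look for a direction elsewhere.** Sections 5.1, 5.4, 7.2 and 7.3 mention the questionnaire by topic only, and 10.1 gives no coding. By contrast, the pain item in 5.3 prints its direction, with 1 as no pain and 10 as the worst. The favourable reading of *Very good* rests on the item's place under the adhesion heading and on the rationale in 5.4. It is an inference, though a reasonable one.

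**Step 3. Size of the effect if some subjects reverse the scale.** The plan gives no figure to reproduce, so this is an illustration. Assumptions: categories scored 1 to 5; all 12 subjects (5.1) complete; the same true product difference d in each; k subjects mirror the scale consistently, so that a score x becomes 6 − x and their difference becomes −d. The value of k has no source in the documents.

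Mean difference = [(12 − k)·d + k·(−d)] / 12 = d·(1 − 2k/12)

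| k | 1 − 2k/12 |
|---|---|
| 0 | 1.00 |
| 1 | 0.83 |
| 2 | 0.67 |
| 3 | 0.50 |
| 6 | 0.00 |

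The sign changes only for k above 6.

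**Step 4. Number of answers exposed.** Section 5.1 expects wear "equal to at least 3 baseplates + tape change in each period", with three periods and 12 subjects.

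- At 3 changes per period: 12 × 3 × 3 = 108 answers. If one of the three is the removal at the visit, 12 × 3 × 2 = 72 are given at home.
- At 4 changes per period (9 days / 2-day wear = 4.5, rounded down): 12 × 3 × 4 = 144 answers, of which 12 × 3 × 3 = 108 at home.

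Withdrawals or less frequent changes would lower these counts. They show how often the item is asked, not how often it is misread.

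**The case against.** The strongest reply is that full reversal is unlikely. The anchors are words, and a subject would have to call a lifted edge *Very good*. The other five 5-point scales all run from unfavourable to favourable, which points the same way. Awkward wording may produce hesitation or noise more readily than a mirrored answer. This stands, and it is why the conclusion is limited to uncertainty and the calculation is only an illustration.

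Second, the text shown in the app is not in the documents. Recruitment is from a Danish user database, so the line in 5.3 may not be what subjects read. This also stands: the finding is secure for the plan's wording and unverified for the data.

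Third, there are safeguards. Section 7.2 has the investigator and, at home, the subject act "before removing, mark the lifted tape area with a pen on the adhesive part", so answers can be set beside a physical record of lift for the same tape. There are also interviews at visits, staff follow-up on app use, listings, a data review meeting, and documented omission of invalid data points. Gross reversal might be noticed. However, no safeguard is directed at this item, the pen mark shows only lift present at removal, and omission helps only once a reversal has been recognised.

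Fourth, the anchors rather than the question could be the slip, since they repeat those of the item just above. Either could be changed. Keeping the anchors preserves a favourable high end across all six scales.

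**Conclusion.** The concern holds. As written, the edge lift/roll item pairs an occurrence question with quality anchors, and nothing in the plan states its direction. *Very good* probably means little lifting, so the scale is not shown to be reversed; its meaning is simply not fixed.

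The consequence is modest. Under the assumptions above, one to three reversed readers among 12 would leave 83% to 50% of the true mean contrast on this item, with its direction unchanged. The number of reversed readers is unknown and may be zero. The damage is limited to one descriptive secondary item in a pilot without pass/fail criteria, and the primary endpoint does not depend on it. It should still be corrected, because the item is reported by product in its own right and the correction is cheap. Confidence is medium, mainly because the app wording cannot be seen.

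**What to change.** Keep the anchors and reword the question in 5.3 and in the app so that the two agree, for example: *How well did the edge of the tape stay attached, without lifting or rolling, during use?* Add one sentence to 10.1 stating that a higher score means less lifting. Check the app text, in the language subjects see, against the revised item.

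If data already exist, leave the item as it was asked. Report it by response category, print the exact wording subjects saw, and read it beside the marked lifted area on the collected tapes. This may be the route that applies: the cover date (12/11/2020) is later than the planned completion of the last subject in 5.8 (06/2020).

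The prospective change costs one line in 5.3, one sentence in 10.1 and one app text, with no added visits, subjects or measurements. It carries an amendment burden. Section 12 requires signed agreement of sponsor and principal investigator and a change-log entry, and counts changes to endpoints or assessment methods as significant, with notification and possibly prior approval. Section 15.1 sends any amendment to the ethics committee and regulatory authority. The reporting route changes only how this one item is presented.
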